**Table 9 Width of 95% CI of estimated IRR by sample sizes and effect sizes**

Effect size: IRR (ratio a/b)	Sample size in person-years (PY), per exposure group							
	150 PY	200 PY	250 PY	300 PY	350 PY	400 PY	450 PY	500 PY
0.5	0.202	0.174	0.155	0.141	0.131	0.122	0.115	0.109
0.7	0.254	0.219	0.195	0.178	0.164	0.154	0.145	0.137
0.9	0.304	0.262	0.234	0.213	0.197	0.184	0.173	0.164
1	0.328	0.283	0.253	0.230	0.213	0.199	0.187	0.178

Note: IRR: Incidence rate ratio; PY: person-years

Under the assumptions described above, to have a level of precision where the width of 95% CI is no larger than 0.2, a minimum size of 350 person-year is required to detect a small effect (i.e., a rate ratio of 0.9). A sample size larger than that will further increase the level of precision.

No justification of the sample size was performed for the comparative analyses specified in the primary objective 2 (40).

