**Study Size:**

All patients available in the databases will be included in the study population. Based on the feasibility assessment, 14,362 patients meeting inclusion criteria and using OM-85 are available in Belgium, 3,219 patients in Italy, and 8,656 patients in China. The study size is based on including the maximum number of patients. However, the strategy to include patients to this study using the TTE framework is not identical to the feasibility assessment, and fewer OM-85 exposed patients will be included in this full study using the TTE framework.

For primary objective 1, the study size required to estimate the difference between rates of two groups (pre- and post- OM-85 treatment) is evaluated based on the level of precision and effect size. With a hypothetical population rate of two episodes per person per year in the baseline and assuming an equal person-time in the two groups (i.e., pre and post treatment), a minimum size of 350 person-years is required to detect a small effect (i.e., an incidence rate ratio of 0.9) with the level of precision where the width of the 95% confidence interval (CI) is no larger than 0.2. No justification of the sample size was performed for the comparative analyses in the primary objective 2.

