### 3.5 Study Size

In this non-interventional study, all patients available in the databases will be included in the study population. Based on the feasibility assessment, 14,362 patients meeting inclusion criteria and using OM-85 are available in Belgium (of which 10,555 patients aged  $\geq 18$  years old), 3,219 patients in Italy (of which 2,742 patients aged  $\geq 18$  years old), and 8,656 patients in China (of which 1,338 patients aged  $\geq 18$  years old). The study size is based on including the maximum number of patients for the OM-85 group. However, the strategy to include patients to this study using the TTE framework is not identical to the feasibility assessment, and fewer OM-85 exposed patients will be included in this full study using the TTE framework ([Section 3.9.5](#)).

For primary objective 1, the study size required to estimate the difference between rates of two groups (pre- and post- OM-85 treatment) is evaluated based on the precision of the point estimate, as described below.

The CI for point estimate of incidence rate ratio (IRR) is calculated as follows ([38](#)), where a and b are the counts of events in each group, PT1 and PT2 are the person-time (in person-years [PYs]) in each group, and F is a quantile of the F distribution.

$$\widehat{\text{IRR}} \text{ CI} = \left( \frac{PT_2}{PT_1} \right) \left( \frac{a}{b+1} \right) \frac{1}{F_{\alpha/2, 2(b+1), 2a}} \text{ to } \left( \frac{PT_2}{PT_1} \right) \left( \frac{a+1}{b} \right) F_{\alpha/2, 2(a+1), 2b}$$

With a hypothetical population rate of 2 episodes per person per year in the baseline (based on reported Upper RTI global age-standardised incidence rate of 225,505 per 100,000 person-years, in the Global Burden of Diseases, Injuries, and Risk Factors Study [GBD] 2019 ([39](#))), and assuming equal person-time in the two groups, the width of the 95% CI for the estimated IRR under difference effect sizes and sample sizes are demonstrated in [Table 9](#).

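### The 350 person-years in Section 3.5 meet a CI-width criterion for an IRR of 0.9, but both the section and the synopsis call this the size needed to detect it; at that size two-sided power is about 48%

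*Protocol*

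**What the plan says.** Section 3.5 states that the size for primary objective 1 "is evaluated based on the precision of the point estimate". Its inputs are a baseline rate ("With a hypothetical population rate of 2 episodes per person per year in the baseline"), a person-time ratio ("assuming equal person-time in the two groups") and an F-quantile confidence interval for the ratio of two counts. Table 9 then gives "the width of the 95% CI for the estimated IRR" for four effect sizes and eight sizes, with columns headed "Sample size in person-years (PY), per exposure group".

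Below Table 9 the criterion is "to have a level of precision where the width of 95% CI is no larger than 0.2", and the conclusion is that "a minimum size of 350 person-year is required to detect a small effect (i.e., a rate ratio of 0.9"). The Study Size paragraph of the synopsis repeats it: "a minimum size of 350 person-years is required to detect a small effect". Neither place gives a power, a test or the confidence limits behind the widths. Section 3.5 adds that no sample size justification was made for primary objective 2, so this is the only sizing statement for a primary objective.

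**The concern.** A limit on interval width and the ability to detect an effect are different properties. To a statistical reader, detecting a rate ratio of 0.9 means a good chance that the result excludes 1 when 0.9 is true. Section 3.7.1 strengthens that reading, because it plans p-values as well as confidence intervals for these models. An interval 0.2 wide around 0.9 reaches roughly to 1, so the criterion by itself cannot deliver detection. Table 9 prints widths without limits, so the reader cannot see this.

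At stake is how the planning statement is understood: it claims for 350 PY a property that this size does not have.

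**Working it through.** **Inputs, all from Section 3.5 and Table 9.** Baseline rate 2 per PY; IRR 0.9; 350 PY in each period; two-sided 95% level. Expected counts:

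- before: b = 2 × 350 = 700
- after: a = 0.9 × 700 = 630

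**Step 1: reproduce the plan's figure.** With PT1 = PT2 the printed formula becomes

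- lower limit = [a/(b+1)] / F(0.975; 2(b+1), 2a)
- upper limit = [(a+1)/b] × F(0.975; 2(a+1), 2b)

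For a = 630 and b = 700 this gives 0.8069 to 1.0037, a width of 0.197, which is the Table 9 cell. All 32 cells match to three decimals. At IRR 0.9 the width is 0.213 at 300 PY and 0.197 at 350 PY; on a finer grid it first falls to 0.2 or below at 340 PY. So 350 PY is correctly the first tabulated size that meets the criterion.

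**Step 2: does that interval exclude 1?** No. The upper limit is 1.004. The expected interval first excludes 1 at 375 PY per period (0.810 to 0.99996).

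**Step 3: power at 350 PY.** For the log rate ratio:

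- SE = √(1/630 + 1/700) = 0.0549
- |ln 0.9| / SE = 0.1054 / 0.0549 = 1.92
- two-sided 5% power ≈ Φ(1.92 − 1.96) ≈ 0.48

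A simulation of 400,000 Poisson pairs gave 48.2% for the Wald and score tests and 47.1% for the protocol's exact interval.

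**Step 4: size needed to detect 0.9.** PY per period = [(1.96 + z)/ln 0.9]² × (1/1.8 + 1/2), where z is the normal quantile of the power:

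- 80% (z = 0.842): about 746 PY
- 90% (z = 1.282): about 999 PY

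The largest size in Table 9, 500 PY, gives 63%. No tabulated size reaches 80% power for 0.9.

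**Step 5: variants.**

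| Change | 95% CI at IRR 0.9 | Power |
|---|---|---|
| As planned, 350 v 350 PY | 0.807 to 1.004 | 48% |
| One-sided 5% test | – | 61% |
| Cited 2.255 per PY instead of 2 | 0.812 to 0.997 | 53% |
| 350 PY before, 700 PY after | 0.820 to 0.989 | 61% |

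None reaches 80%. For context, 350 PY per period gives about 83% power for an IRR of 0.85 and 98% for 0.8. The problem is confined to the effect size that the sentence names.

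**The case against.** The best defence is that this is an estimation plan and *detect* is a loose verb. Section 3.5 announces a precision basis, the disputed sentence opens with the width criterion, and the next one again speaks of precision. The checklist in Appendix 2 marks the item on hypotheses to be tested as not applicable. The upper limit passes 1 by only 0.004 and drops below it with the cited rate of 2.255. All of that stands, and it makes this a wording error. It does not rescue the word: power is 48% with the planned rate and 53% with the cited one.

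A reader might be tempted to go further in four ways that the document does not support.

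- **That Table 9 or the 350 PY is miscalculated.** Both are correct as precision statements.
- **That assuming equal person-time flatters the design because follow-up runs to 24 months.** Primary objective 1 compares 12 months before with both 12 and 24 months after. Equal time suits the first comparison. For the second, more time after initiation narrows the interval and raises power, so the assumption is conservative.
- **That over-dispersion makes the shortfall much larger.** The protocol gives no dispersion figure. The comparison is within the same patients, with cluster-robust errors, so stable differences between patients largely cancel. A simulation of 350 patients with a frailty shared across both periods (dispersion 0.5 and 1.0) left power at 48–49%. Power falls, to 28% and 21%, only if the periods are treated as independent. Variation within a patient over time could still matter, but the document gives nothing to size it.
- **That 350 PY will be used to call country or subgroup results adequately sized.** Nothing in the protocol does this. Section 3.2.2.3 runs subgroups only where counts allow, and Section 3.9.5 says random error will be discussed from the numbers and follow-up obtained.

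**Conclusion.** The sizing arithmetic is right and the conclusion drawn from it is misworded in two places. At 350 PY per period a true IRR of 0.9 would fail to reach two-sided 5% significance about half the time, and the expected interval touches 1. This rests on the protocol's 2 episodes per PY, equal person-time and independent Poisson counts; with twice the person-time after initiation, power is about 61%.

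The practical effect is small. All available patients enter, and the feasibility counts are 3,219 (Italy), 8,656 (China) and 14,362 (Belgium) OM-85 users. The protocol expects fewer in the study, by an amount it does not state. If each patient contributes about 1 PY per period, 1,000 retained initiators in a country already give about 90% power under the Poisson assumption. The statement should be corrected because it is untrue as written; the design itself is not shown to be too small.

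**What to change.** In Section 3.5 below Table 9, and in the Study Size paragraph of the synopsis, drop *detect*. Say that 350 PY per period estimates an IRR of 0.9 with a 95% CI no wider than 0.2, about 0.81 to 1.00, and that this interval does not exclude 1.

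If the sponsor wants to keep a detection claim, state it with its power: about 750 PY per period for 80% or about 1,000 PY for 90%, two-sided 5%, assuming Poisson counts, 2 episodes per PY and equal person-time.

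The cost is one sentence in each place. Table 9, the analysis and enrolment stay as they are. No power threshold for reading country or subgroup results is needed: the plan is estimation-based, and the observed intervals will show the precision achieved.

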## 3.6 Data Management

### 3.6.1 Data Processing

The data from Belgium, Italy, and China will be processed separately.

THIN will extract the individual-level data from the Italian and Belgian datasets and transfer anonymised individual-level data to Parexel. THIN has built on a common data model, which is mapped to the format of the OMOP. Parexel will process and analyse the individual-level data.

In China, local data protection regulations prevent Parexel from directly accessing and processing individual-level data. Consequently, a local partner, Inspur, will process the individual-level data and conduct the data analysis under Parexel's guidance and supervision. The extracted individual-level data will be securely transferred to a local server maintained by Inspur. Inspur will supervise the data extraction and conduct the data analysis under the supervision of Parexel. As part of the data analysis process, Inspur will address any queries or corrections necessary. It is of utmost importance that all amendments made to the data are diligently recorded by Inspur, along with the corresponding dates of these revisions. Inspur will transfer study results as aggregate-level data to Parexel.

### 3.6.2 Archiving Study Records

According to International Society for Pharmacoepidemiology Guidelines on Good Pharmacoepidemiology Practices (GPP), the study archive should be maintained for at least 5 years after final report or first publication of study results, whichever comes later. The archive should include all source data. However, as source data extracted from THIN Italy and Belgium will be licenced for 12 months, those will be kept for one year before destruction.

### 3.7 Data Analysis

A separate SAP will be produced, providing detailed methods for the analyses outlined below. Any deviations from the planned analyses will be described and justified in the final study report.

For analyses conducted by Parexel using THIN data, SAS® version 9.4 or higher (SAS Institute, Cary, NC, US), and R will be used to conduct analyses and generate tables, listings, and figures in a secure environment, unless otherwise specified in the SAP. For analyses conducted by Inspur in China, R will be used to conduct analysis and generate tables, listings, and figures within the Inspur environment.

The analyses will be conducted separately in Belgium, Italy, and China. Conducting a summarised analysis combining the results of the countries for some of the objectives may be considered in the SAP. The appropriateness of combining the results would be considered, including heterogeneity between the databases (41).

#### 3.7.1 General Considerations

For descriptive statistics, continuous data will be summarised using descriptive statistics (number of non-missing values, mean, median, the first quartile, the third quartile, standard deviation [SD], minimum, and maximum). Categorical data will be summarised using frequency tables (frequencies and percentages) among patients with non-missing values.

The number and percentage of missing data will be presented as a separate category for all variables in the descriptive statistics. For the comparative analysis, only observations with complete data will be used. Multiple imputation might be considered for selected variables after the evaluation of missingness. The handling of missing data will be described in more detail in the SAP.

From the overall study population, patients will be assigned to the exposure groups (OM-85 or SOC/non-user group) as detailed in [Section 3.3.1](#). Thereafter, PS will be applied to match the OM-85 initiators to comparable SOC/non-user patients, to account for measurable baseline confounding factors between the compared groups. PS of being included in the exposure group initiating OM-85 as opposed to being included in the SOC/non-user group will be estimated for each patient using logistic regression model. Confounding factors available in the databases will be evaluated for inclusion as covariates in the logistic model, including but not limited to patient demographics, BMI, history of RTI (including upper vs lower), comedications, comorbidities, clinical characteristics, duration of RTI-related hospitalisation(s), and calendar year of CED (see [Section 3.3.3](#); to be detailed in the SAP). Histogram of the PS for both exposure groups will be generated to visually evaluate if there is substantial overlap. Nearest-neighbour matching based on the PS will be used to form pairs of patients from each exposure group that are comparable in baseline confounding factors. The applied matching ratio will be defined in the SAP.

Comparative analysis comparing outcomes measured before and after OM-85 initiation will be performed in all patients assigned to OM-85 exposure group. The distribution of the outcomes measured before and after OM-85 initiation (including various follow-up windows per specified in each objective) will be presented. Generalised linear models will be used, with the flag that indicates before or after OM-85 initiation as the independent variable and the outcome of interest as dependent variable.

Comparative analysis comparing the two exposure groups (treatment strategies, i.e., OM-85, or SOC/non-user) will be performed among the PS-matched samples. The distribution of the outcomes measured in each exposure group and in various follow-up windows as specified in each objective will be presented. Generalised linear models will be used, with the flag that indicates exposure group assignment (i.e., OM-85 or SOC/non-user) as the independent variable and the outcome of interest as dependent variable.

For all the generalised linear models used, distribution and link functions that are appropriate to the type of outcome will be used. Offset will be applied when applicable. Estimated coefficients (or corresponding exponentiated estimates, e.g., IRR) of the independent variables with corresponding 95% CI and significance level (i.e., p-value) will be reported. Cluster-robust standard errors will be used in estimating CI and significance level, to account for correlated data.

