**Data Analysis:**

The analyses will be conducted separately in Belgium, Italy and China. Conducting a summarised analysis combining the results of the countries may be considered.

For descriptive statistics, continuous data will be summarised using descriptive statistics (number of non-missing values, mean, median, interquartile range, standard deviation, minimum, and maximum). Categorical data will be summarised using frequency tables

(frequencies and percentages). Time-to-event data will be summarised using the Kaplan-Meier estimate.

From the overall study population, patients will be assigned to the exposure groups (OM-85 or SOC/non-user group) according to whether they received treatment at CED or during the 30-day initiation grace period. Thereafter, PS will be applied to match the OM-85 initiators to comparable SOC/non-user patients, to account for measurable baseline confounding factors between the compared groups. PS of being included in the exposure group initiating OM-85 as opposed to being included in the SOC/non-user group will be estimated for each patient using logistic regression model.

The number and percentage of patients selected into the overall study population, by meeting all the inclusion criteria (no exclusion criteria applied), will be presented for each data source (country) and separated by exposure group. This will be done before and after applying the PS matching (using 1:1 greedy nearest-neighbour method).

The rate of RTI episodes will be estimated by calculating the total number of RTI episodes observed, divided by the total number of person-time (e.g., person-years) during a period of interest. Rates of RTI episodes will be estimated separately in patients initiating preventive treatment with OM-85 and in the SOC/non-user group. Furthermore, rates of RTI episodes during the baseline period will serve as reference in each treatment group to evaluate the effects of therapy during follow-up.

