- **CED:** The CED is defined during the inclusion period, as the date of the 2nd, 3rd, ... or nth RTI episode during the inclusion period (see inclusion criteria in [Section 3.2.2](#)). This is also the date when a patient fulfils all the eligibility criteria. The CED can occur any time during the inclusion period. If a patient meets the eligibility criteria more than once during the inclusion period, and thereby has several candidate CEDs, the CED used in the study will be selected at random, which is one of the unbiased methods of selection of index date (29). The CED defines the end of the baseline period and the start of the initiation grace period for each included patient.

- **Baseline period:** The baseline period for each included patient is defined as the time before the CED. The minimum baseline period will be 12 months, and the maximum baseline period will be as long as data are available in each country (from January 2005 in Belgium, from January 1994, for GPs and 2017 for paediatricians, in Italy, and from January 2018 in China). The minimum baseline period of 12 months will be used for assessing the RTI rate during the baseline period and other baseline variables ([Section 3.7.4.1](#)). The maximum baseline period (all available data) will be used for selected variables, such as comorbidities (e.g., allergies, myocardial infarction, and cancer, see [Table 8](#)), since these could have occurred earlier but may not have been recorded in the data during the 12-month baseline period. Extending the 12-month baseline period for such variables is expected to improve the accurate classification of them (i.e., decreases the risk of covariate misclassification).
- **Initiation grace period:** For each included patient, a 30-day initiation grace period starting from the CED will be applied, to allow the included patients to initiate OM-85 during a reasonable period after the CED, as it is unrealistic to expect that OM-85 would in clinical practice be prescribed on the date of meeting the eligibility criteria ([28,29](#)).
- **OM-85 initiation date:** The OM-85 initiation date will be the date of the first observed prescription of OM-85 during the 30-day initiation grace period, starting from the CED. This is applicable only for the OM-85 exposure group.

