**Table 4 Inclusion Criteria**

	Inclusion Criteria	Operational Definition
1	Patient aged $\geq 1$ year of age at CED	Aged $\geq 1$ year at CED
2	Patient has $\geq 1$ RTI episodes during the 12-month baseline period prior to CED	$\geq 1$ RTI episodes within a 12-month period during the inclusion period. The CED is the date of the 2 nd , 3 rd , ... or n th RTI episode (i.e., date of fulfilling the inclusion criteria). If one patient has multiple CED during the inclusion period, the CED will be selected randomly. The definition of an RTI episode provided in Section 3.3.2.1
3	Patient has $\geq 12$ months of continuous enrolment in the database prior to CED	$\geq 12$ months of continuous enrolment in the database prior to the CED. Operationally, patients were required to have entered the database at least 12 months before the CED to be included in the study. In THIN (Belgium and Italy), this can be defined by a district variable for entry to the database: first contact date. In Inspur (China), patients are required to have records in the database at least 12 months before the CED (during the 12-month baseline period) to be eligible for inclusion
4	No record of a prescription of any bacterial lysates in the 12-month baseline period prior to CED	No record of the country-specific drug codes ( Appendix 4 ) during the 12-month baseline period

Note: CED: cohort entry date; RTI: respiratory tract infection; THIN: The Health Improvement Network.

Inclusion criterion 2 on the requirement of having  $\geq 1$  prior RTI episodes is important to apply because OM-85 is indicated for prevention of recurrent RTIs (24). However, patients in the SOC/non-user comparator group may still have fewer prior recurrent RTIs than the OM-85 group receiving preventive therapy. Therefore, prior recurrent RTIs will also be used in the PS matching of the compared exposure groups. The impact (preventive effect) of OM-85 on the recurrence of RTIs is anticipated to be higher in patients with an increased recurrence risk (35). Hence, the analyses will also be stratified by the number of RTI episodes prior to CED (see [Table 5](#)).

The inclusion of patients is not defined by sex. Sex is instead defined at CED and considered in the PS.

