### 3.3.3 Other Variables

Selected baseline variables described under outcomes ([Section 3.3.2.2](#)) will be assessed in the Step 1 analysis and will be used for controlling for confounding at baseline, through including the selected variables to the PS and matching OM-85 initiators to non-initiators (SOC/non-user group) using the PS. The following baseline variables will be considered in the PS:

- Patient demographics: Age and sex
- BMI
- RTI history, including type (Upper/Lower/Other) and number of previous RTI episodes
- Comedications
- Antibiotic prescriptions
- Selected comorbidities, especially smoking and respiratory conditions, such as asthma, COPD, and CB
- Overall and RTI-specific healthcare resource utilisation, especially duration of RTI-related hospitalisation(s) as a proxy for severity of prior RTIs
- Calendar year of CED

The confounders applied in the PS will be detailed in the SAP.

Variables used for defining sub-populations are described in [Section 3.2.2.3](#).

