### **3.7.3 Analysis of Primary Endpoint: RTI Rates (Primary Objectives 1-2, Secondary Objectives 3-4, Exploratory Objectives CCI)**

The primary outcome is the rate of RTIs episodes measured during different periods of interest, as specified in the objectives. The rate of RTI episodes will be estimated by calculating the total number of RTI episodes observed, divided by the total number of person-time (e.g., person-years) during a period of interest. Rates of RTI episodes will be estimated separately in patients initiating preventive treatment with OM-85 and in the SOC/non-user group. Furthermore, rates of RTI episodes during the baseline period will serve as reference in each treatment group to evaluate the effects of therapy during follow-up.

Comparative analysis comparing the RTI rates before and after OM-85 initiation, and analysis comparing RTI rates in the two exposure groups will be performed using approaches as described in the General Considerations. Generalised linear models with a Poisson distribution or negative binomial distribution (to account for over-dispersion) will be used to estimate the association between the initiation of OM-85 and the outcome of RTI rates, with the natural logarithm of the time at risk as offset (42).

The analyses will be identical for the exploratory objectives **CCI** **CCI** (Section 3.2.2.3).

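### The between-group model for primary objective 2 uses the baseline RTI count only through the propensity score; adding its log to the outcome model is a nearly free gain in precision, of a size the protocol does not fix

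*Protocol*

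**What the plan says.** Section 3.7.1 fits the between-group comparison in the propensity-score-matched sample and defines its model: "Generalised linear models will be used, with the flag that indicates exposure group assignment (i.e., OM-85 or SOC/non-user) as the independent variable". Section 3.7.3 refers back to this and supplies the family, "Generalised linear models with a Poisson distribution or negative binomial distribution (to account for over-dispersion) will be used", with log time at risk as offset. No other model term is named. Section 3.7.1 plans cluster-robust standard errors for all these models but does not say what the cluster is.

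The baseline count is available for everyone. Section 3.2.1 says: "The minimum baseline period of 12 months will be used for assessing the RTI rate during the baseline period and other baseline variables". Table 4 requires at least one RTI episode in those 12 months, and Table 8 lists the number of episodes as a baseline variable.

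The count is used elsewhere. Section 3.2.2.1 commits to it for matching, "Therefore, prior recurrent RTIs will also be used in the PS matching of the compared exposure groups", and section 3.3.3 lists, among the score variables, "RTI history, including type (Upper/Lower/Other) and number of previous RTI episodes". It shares the score with age, sex, BMI, comedications, antibiotics, comorbidities, healthcare use and calendar year. Table 5 stratifies by it. Section 3.7.3 also says that "rates of RTI episodes during the baseline period will serve as reference in each treatment group to evaluate the effects of therapy during follow-up", which is a within-group use and not a term in the between-group rate ratio. The Synopsis describes 1:1 greedy nearest-neighbour matching; section 3.7.1 leaves the ratio to the SAP.

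**The concern.** A patient's own RTI count over the previous year is likely to be among the best predictors of the count over the next. Two patients matched on one score built from many variables share the score, not necessarily the count. Where they differ, the spread in RTI frequency between patients stays in the residual of a model that holds only the exposure flag. Clustering by pair recovers that precision only as far as pairs agree on the count. Any difference in mean count that greedy matching leaves behind also passes into the rate ratio.

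Primary objective 2 is the comparative-effectiveness answer. It is run by country and may be repeated in five age strata and two prior-RTI strata. A modest true effect is then more likely to be reported as inconclusive than the data require.

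**Working it through.** **Inputs from the protocol.** Baseline rate 2 episodes per person-year, rate ratio 0.9, 95% intervals (section 3.5). Feasibility counts of OM-85 users: 14,362 in Belgium, 3,219 in Italy, 8,656 in China. These are upper bounds, since section 3.5 expects fewer. For objective 2 there is no sample-size justification.

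**Inputs assumed.** Gamma variation between patients with variance k = 0.25, 0.5 or 1; 12 months of follow-up; the closeness of pairs on the baseline count.

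**Step 1: the plan's own figure.** With the F-quantile interval of section 3.5, b = 2 × 350 = 700 and a = 0.9 × 700 = 630, the width is 0.197, as in Table 9. All 32 cells reproduce. The table serves objective 1 and says nothing on objective 2.

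**Step 2: formula without matching.** Variance of the log rate ratio = (1/2 + 1/(2 × 0.9) + 2k)/n. Correlation of baseline and follow-up counts ρ = 2k/(1 + 2k). Adjustment multiplies the variance by 1 − ρ².

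Example, k = 0.5 and n = 1,000 per group: (0.5 + 0.556 + 1)/1,000 = 0.002056, SE 0.0453. Power = Φ(0.1054/0.0453 − 1.96) = 64%. With ρ = 0.5 the SE is 0.0453 × √0.75 = 0.0393 and power is 77%.

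Power, unadjusted → adjusted:

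| n per group | k = 0.25 | k = 0.5 | k = 1 |
|---|---|---|---|
| 500 | 47% → 52% | 38% → 48% | 27% → 44% |
| 1,000 | 76% → 81% | 64% → 77% | 48% → 72% |
| 3,219 | 99.8% → 99.9% | 98.6% → 99.8% | 92.8% → 99.6% |
| 8,656 | 100% → 100% | 100% → 100% | 100% → 100% |

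**Step 3: simulation with 1:1 greedy matching.** At least one baseline episode, Poisson model, pair-clustered SE, 600 runs per cell (Monte Carlo error of each power up to √(0.25/600) = 2 points). Power without → with log baseline count; each cell gives about 450–500 pairs, then about 900–1,000 pairs:

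| Within-pair correlation of the count | k = 0.25 | k = 0.5 | k = 1 |
|---|---|---|---|
| 0.91–0.99 | 57.0 → 57.0; 85.8 → 85.3 | 54.7 → 56.5; 87.5 → 88.0 | 66.3 → 69.5; 90.8 → 92.5 |
| 0.48–0.55 | 57.5 → 60.7; 85.5 → 86.2 | 54.8 → 60.3; 84.0 → 89.0 | 55.2 → 66.5; 83.7 → 92.3 |
| 0.15–0.21 | 51.5 → 59.8; 85.5 → 88.8 | 45.3 → 54.0; 75.2 → 87.0 | 44.7 → 66.0; 73.3 → 90.5 |

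The gain is about 0 to 3 points when pairs agree closely on the count, 1 to 11 in the middle, and 3 to 21 when they agree loosely.

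**Step 4: score estimated from the data.** 750 pairs, 1,000 runs, score on the log count plus five covariates unrelated to it, within-pair correlation 0.07–0.09:

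| k | Unadjusted SE / true SD | Power at 0.9, unadjusted → adjusted | Test size at 1.0, unadjusted → adjusted |
|---|---|---|---|
| 0.25 | 0.042 / 0.041 | 68% → 74% | 4.2% → 4.9% |
| 0.5 | 0.045 / 0.041 | 60% → 75% | 3.4% → 4.7% |
| 1.0 | 0.048 / 0.042 | 50% → 80% | 3.2% → 5.7% |

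Here the unadjusted SE is too large and the test conservative. In Step 3 the pair-clustered SE broadly agreed with the empirical SD, so the overstatement depends on how the score is built. With five score covariates correlated with the count (within-pair correlation about 0.87), adjustment cut the SE by only about 1% (k = 0.25), 3% (k = 0.5) and 6–9% (k = 1).

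**Step 5: residual imbalance.** Without a caliper, the unadjusted log rate ratio was off by 0.002–0.013 in the Step 4 runs, towards no benefit. With a small control pool the bias was 0.003–0.056, and adjustment largely removed it. For scale, |ln 0.9| = 0.105.

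**The case against.** The strongest reply has four parts.

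- **SAP detail.** Section 3.7 leaves detailed methods to the SAP, section 3.9.1.2 leaves further confounding analyses to it, and the word *only* does not appear. This stands in part: the SAP may add covariates. But where the protocol defers a specific choice (score variables, matching ratio, missing data) it says so. For this model it names the independent variable and attaches no such deferral.
- **The count is already used.** This is true, and a marginal model after matching with cluster-robust errors is a recognised method. A reader might infer that the protocol ignores baseline RTI frequency; it does not. What remains is that a scalar score may pair the count loosely.
- **Imbalance after matching is not shown.** A reader might take the remark in section 3.2.2.1 that non-users may have fewer prior RTIs as evidence of it. That remark describes patients before matching and is the reason given for matching. Caliper and control-pool size are not known.
- **At the feasibility counts it hardly matters.** At a rate ratio of 0.9 this is right for Belgium and China, and for Italy unless k is high. Those counts are upper bounds, however. Italy has at most 3,219 − 2,742 = 477 users under 18, across three paediatric strata. Subgroup analyses are conditional in section 3.2.2.3.

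**Conclusion.** The point holds as a cheap improvement. As written, the between-group model has one independent variable, while the outcome's own baseline value is available for every patient and used only through the score. In the checks above, adding it did not materially widen the interval and often narrowed it.

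The size cannot be read from the documents. It runs from about 0 to 20 power points or more (30 in the most extreme simulated cell), depending on over-dispersion, closeness of pairs on the count, and the number of pairs. It is near 0 when the score is driven by the count, or with several thousand pairs at a rate ratio of 0.9 and moderate over-dispersion.

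Two stronger readings are tempting. One is that the intervals are definitely too wide, with a fixed loss such as 5 to 14 points. That needs an assumed correlation of about 0.35 to 0.60 at 80% unadjusted power in the formula without matching, and the protocol gives neither figure. The other is that inference is invalid. Under loose matching the simulated unadjusted pair-clustered SE was about right or too large, with test size 3.2% to 4.2%; nothing points to false positives from this source.

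**What to change.** In sections 3.7.1 and 3.7.3, state that for primary objective 2 and secondary objective 4 the model in the matched sample contains the exposure flag and the log of the 12-month baseline RTI episode count. Keep the log person-time offset and the cluster-robust standard errors, and name the matched pair as the cluster. Report the unadjusted matched rate ratio as supportive. Settle this before outcomes are analysed, so that the covariate is not chosen after seeing results.

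The cost is one sentence and one model term. No new data are needed, since the count is already derived for the score, Table 8 and the strata, and its log is defined because every patient has at least one episode. The target remains a rate ratio on the log link. The small downside is reliance on a log-linear baseline term, which the supportive unadjusted estimate lets a reader check.
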